# **3. STUDY PLAN AND PROCEDURES**

## **3.1 Overall Study Design and Flow Chart**

This study will include the subjects who enrolled in DACAB trial to compare clinical outcomes 5 years after CABG. After completing 12-month randomized treatment from DACAB trial, investigators would not make any interventions or impact on subjects' therapeutic strategy.

Aspirin monotherapy would be given to most subjects according to the current guidelines. However, other antiplatelet regimens might be given for subjects by their attending physician based on the subject's individual condition. Subjects would spontaneously undergo regular laboratory test such as biochemical parameters, ECG, UCG, coronary computed tomography angiography imaging (CCTA) or coronary angiography (CAG) and clinical follow-up according to clinical need and their individual condition. At 5-year ( $\pm$  3 month) after CABG, a face-to-face visit is scheduled to be performed to collect the occurrence of clinical events, including types and time of events. The first 5-year visit would be performed around August 2019.

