## **5. COLLECTION OF STUDY VARIABLES**

### **5.1 Recording of Data**

The investigator will ensure that the data is recorded on the paper form of Case Report Forms (CRF) as specified in the study protocol and in accordance with the instructions provided.

General information such as subject's age and gender, medical history should be recorded. Medical record and laboratory test, such as biochemical parameters (cardiac troponin, brain natriuretic peptide, etc.), ECG, UCG, CT/MRI, coronary CTA or coronary angiography related to the end points of this study will be collected and recorded to assist in the determination of endpoint events.

The investigator ensures the accuracy, completeness, and legibility of the data recorded and of the provision of answers to data queries according to the Clinical Study Agreement. The investigator will sign the completed paper CRF. A copy of the completed paper CRF will be archived at the study site.

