## **5.2 Data Collection at 5-year Visit**

The data of subjects will be collected at the visit at 5-year ( $\pm 3$  month) after CABG. The collected data includes: vital signs; current medications; types and time of events; original medical record and laboratory test results related to clinical events. For deceased patients, the death and cause of death will be determined by telephone interview with their relatives firstly. The related medical records would be acquired from their relatives to further determination the cause of death, if available. Electronic medical records would be approached under relatives' permission. Determination of graft patency will be determined from medical records. Original images of coronary CTA or coronary angiography will be acquired and re-assessment.

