### **9.3 Determination of Sample Size**

A total of 500 subjects were randomized in DACAB study (ticagrelor + aspirin, 168; ticagrelor alone, 166; aspirin alone, 166). There are 5 subjects died before 12-month visit, of these, 2 died in ticagrelor + aspirin group, and 3 died in aspirin alone group. Therefore, 495 patients would be scheduled for 5-year on-site visit.

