4.2 Secondary Outcome

- MACE-5, defined as a composite of all-cause death, myocardial infarction, stroke, coronary revascularization and hospitalization for unstable angina. The outcome measure is the time to the first occurrence of MACE-5 event from randomization to the last visit;
- MACE-3, defined as a composite of cardiovascular death, myocardial infarction and stroke. The outcome measure is the time to the first occurrence of MACE-3 event from randomization to the last visit;
- All-cause death. The outcome measure is the time to the first occurrence of all-cause death from randomization to the last visit;
- Cardiovascular death. The outcome measure is the time to the first occurrence of cardiovascular death from randomization to the last visit;
- Myocardial infarction. The outcome measure is the time to the first myocardial infarction from randomization to the last visit;
- Stroke. The outcome measure is the time to the first stroke from randomization to the last visit;
- Coronary revascularization. The outcome measure is the time to the first coronary revascularization from randomization to the last visit.;

- Hospitalization for unstable angina. The outcome measure is the time to the first hospitalization for unstable angina from randomization to the last visit;
- Graft failure/vein graft failure at the last visit (Fitzgibbon Grade B/O assessed by CCTA or CAG). The outcome measure is the incidence of graft failure/vein graft failure.

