6.2.4 Secondary Outcome

The time to event variables in the secondary outcomes will be analyzed similarly with the primary outcome.

As 1-4 vessels were generally measured in each subject, the vein graft patency at 5 years after CABG is a categorical data measured repeatedly in subjects. The number and the percentage of the grafts in Fitzgibbon grade B/O will be summarized by the group in previous DACAB study. GEE (Generalized Estimating Equations) was used to compare the subjects' saphenous vein graft patency rate among groups.

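### The graft-patency GEE names no weights or covariates although no scan is scheduled after month 12; imaging that follows the 1-year graft grade can bias both patency and the arm difference, even if the arms are truly equal at 5 years

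*SAP*

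**What the plan says.** **Outcome.** SAP 4.2 lists "Graft failure/vein graft failure at the last visit (Fitzgibbon Grade B/O assessed by CCTA or CAG" as a secondary outcome. SAP 6.2.4 speaks of vein graft patency at 5 years, and Table 13 reports a 1-5 year rate.

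**Source of the images.** Protocol 3.1 says "Subjects would spontaneously undergo regular laboratory test such as biochemical parameters, ECG, UCG, coronary computed tomography angiography imaging (CCTA) or coronary angiography (CAG". The rest of that sentence makes the timing a matter of ordinary care: "and clinical follow-up according to clinical need and their individual condition". The data list for the 5-year visit in Protocol 5.2 contains no scan: "The collected data includes: vital signs; current medications; types and time of events; original medical record and laboratory test results related to clinical events". The same section adds "Determination of graft patency will be determined from medical records", and Protocol 5.1 says that "coronary CTA or coronary angiography related to the end points of this study will be collected and recorded".

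**Analysis.** SAP 6.2.4: "GEE (Generalized Estimating Equations) was used to compare the subjects' saphenous vein graft patency rate among groups". The note to Table 13 says that the rate difference, RR and p value come from GEE. Neither place names weights, covariates or a sensitivity analysis. SAP 6.2.1 assumes data missing at random and imputes nothing unless specified. Table 11 tabulates examined and not examined patients, and scan time, by arm. Confounder adjustment is planned for the 1-year graft-failure cohorts (6.2.9), and GLM and propensity score methods for the subgroup cohorts (6.2.10), but neither for this arm comparison.

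**The concern.** A GEE that contains only arm estimates patency among imaged patients. It carries over to all patients only if, within each arm, being imaged is unrelated to patency. The missing-at-random statement does not secure this. If imaging depends on the 1-year grade, and on nothing else related to later patency, the data are missing at random given that grade. The GEE leaves the grade out and is still biased.

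A graft that failed at 1 year is likely to be failed later, so the 1-year grade is the obvious variable that could drive both imaging and outcome. The study already holds it: it defines the cohorts in SAP 6.2.9, and Table 32 relates it to patency at 1-5 years.

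At stake is whether Table 13 can be read as showing that the 1-year patency advantage persisted, shrank or grew, or whether part of that pattern comes from who was imaged.

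**Working it through.** The plan gives no imaging rate or expected 5-year patency, so there is no figure of its own to reproduce. The calculation shows what the planned GEE would report under stated assumptions.

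**Inputs from the documents**
- Year-1 vein graft patency *p* (Protocol 1.1, SAP 1): 88.7% for T+A, 76.5% for A. The fractions printed beside T and A give each other's percentage (371/485 = 76.5%, 404/488 = 82.8%); the percentages were used.
- Arm sizes 168 and 166. Vein grafts per patient: 487/168 = 2.90, 485/166 = 2.92, 488/166 = 2.94, so 3 were used.

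**Assumptions**
- A graft patent at year 1 is still patent later with probability *s* = 0.85; a failed graft does not recover.
- Year-1 status is beta-binomial within patient, ICC 0.2 to 0.6.
- A patient is imaged with probability *a* after any year-1 failure and *b* otherwise, in both arms alike. Scan timing is not modelled.

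**Formulas**
- Chance that all three grafts are patent at year 1, with k = 1/ICC - 1: Z = [pk(pk+1)(pk+2)] / [k(k+1)(k+2)].
- True patency = s × p.
- With 3 grafts each, the GEE estimate equals the proportion among imaged patients: s × [bZ + a(p - Z)] / [bZ + a(1 - Z)]. Only the ratio a/b matters.

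**Truth.** 0.85 × 0.887 = 75.4%; 0.85 × 0.765 = 65.0%; difference 10.4 points; RR 1.16.

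**One case in full (a = 0.7, b = 0.4, ICC 0.2, k = 4)**
- T+A: Z = 3.548 × 4.548 × 5.548 / 120 = 0.746. GEE: 0.85 × (0.2984 + 0.0987) / (0.2984 + 0.1778) = 70.9%.
- A: Z = 3.060 × 4.060 × 5.060 / 120 = 0.524. GEE: 0.85 × (0.2096 + 0.1688) / (0.2096 + 0.3333) = 59.2%.
- Difference 11.6 points against a true 10.4.

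**Equal 5-year patency.** Keep the year-1 figures but set both arms to 65.0% later, so *s* for T+A is 0.6503/0.887 = 0.733. T+A then reads 0.733 × 0.3971/0.4762 = 61.1% and A 59.2%: a false difference of 1.9 points.

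**All cases (first figure ICC 0.2, second ICC 0.6)**

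| Imaged with / without year-1 failure | T+A reads (true 75.4%) | A reads (true 65.0%) | Difference (true 10.4) | Difference if both truly 65.0% |
|---|---|---|---|---|
| 70% / 40% | 70.9, 70.2 | 59.2, 57.3 | 11.6, 12.9 | +1.9, +3.2 |
| 60% / 40% | 72.2, 71.8 | 60.8, 59.5 | 11.4, 12.3 | +1.5, +2.4 |
| 50% / 40% | 73.7, 73.5 | 62.7, 62.0 | 11.0, 11.5 | +0.9, +1.4 |
| 40% / 70% | 78.8, 79.1 | 70.7, 71.6 | 8.2, 7.5 | -2.7, -3.4 |

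**Inference (simulated trials of 168 vs 166).** When the true difference is 10.4, 95% CI coverage is about 92% to 94% at 70%/40% and 89% to 91% at 40%/70%. When both arms are truly 65.0%, the two-sided 5% test rejects in about 7% to 9% of trials at 70%/40% and about 10% to 13% at 40%/70%.

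**Sensitivity to the assumptions**
- If 10% to 30% of failed grafts are later read as patent, bias in the difference at 70%/40% falls from 1.3-2.5 to 0.8-2.2 points.
- If A were 82.8% at year 1, a true 5.0-point difference reads 5.9 to 6.5 at 70%/40%.
- A separate simulation with 2 to 4 grafts, 90% retention and ICC 0.35 gave the same pattern: 11.1 became 13.1 at 80%/40% and 7.8 at 40%/80%.

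**Effect of weighting.** Weights from the year-1 grade return 75.4% vs 65.0%, as they must when that grade alone drives imaging. If a new failure also adds 20 points to the chance of imaging, weighting still understates patency by 2.6 to 3.2 points (plain GEE: 6.5 to 8.0). If 20% to 50% of imaged patients with a failed graft are then revascularized, adding undated revascularization to the imaging model gives 76.3% vs 65.7% up to 78.2% vs 67.3%. It introduces error rather than removing it.

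**The case against.** The strongest reply is that nothing shows imaging followed the 1-year grade. Protocol 3.1 calls the tests regular, so routine surveillance scans are possible, and within-arm selection could be slight. At 50%/40% the bias in the difference is only about 1 point, against a sampling SD of roughly 5 points. This stands. A reader might infer that Table 13 is necessarily biased, or biased in favour of T+A; the documents do not support that, because they give no imaging rates and the sign reverses when the rates do.

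A second reply is that randomized arms sharing one imaging rule leave the test valid when there is no true difference. A reader might infer this, but it holds only if the arms have the same patency at year 1 as well as later. DACAB reported 88.7% vs 76.5% at year 1, so it does not cover this trial.

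A third is that Table 11 already discloses who was scanned. It does so by arm, not by 1-year grade, so it cannot show the selection at issue.

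A fourth is that weighting depends on its model and cannot capture unrecorded symptoms that prompt a scan. That is true. It is why weighting belongs in a sensitivity analysis, with a tipping-point analysis beside it.

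**Conclusion.** The point holds as a conditional one. If imaging after month 12 depends on the 1-year grade, the planned GEE can misstate absolute patency and the arm difference, even under missing at random, and even with equal 5-year patency and one imaging rule.

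Under the stated assumptions, 70%/40% imaging understates patency by 4.5 to 7.8 points and moves a true difference of 10.4 to between 11.6 and 12.9. At 40%/70% the difference reads 8.2 to 7.5. With equal 5-year patency, the false difference is +1.9 to +3.2 or -2.7 to -3.4 points respectively. Barring chance cancellation, bias in the difference is close to zero only if imaging is unrelated to patency within arm, or if the arms share year-1 patency, later patency and one imaging rule.

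Size and direction rest on assumed imaging rates, graft retention and within-patient correlation. The mismatch between last visit, 5 years and 1-5 years needs no assumption. Only a secondary outcome is affected; MACE-4 is not. The change should be made, but the primary conclusion does not depend on it.

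**What to change.** In SAP 4.2, 6.2.4 and Tables 11 and 13:

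1. Keep the plain GEE, labelled *imaged patients only*. Beside it, as a sensitivity analysis, report a GEE weighted by the inverse probability of imaging, or multiple imputation, using arm, baseline factors and the 1-year grade with a level for missing. Leave out revascularization and other events that follow from the scan.
2. State the target population, for example FAS patients alive at month 12 (Protocol 9.3: "495 patients would be scheduled for 5-year on-site visit"). Report by arm how many died unscanned, since their later patency is undefined.
3. Split Table 11 by 1-year grade as well as by arm. This is the cheapest direct check on whether the concern applies.
4. Use one time window in 4.2, 6.2.4 and Table 13.
5. Add one simple tipping-point analysis that shifts the odds of patency in unscanned grafts, because weighting on the 1-year grade does not remove selection on current symptoms.

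**Cost.** SAP wording and moderate programming; no new scans or data. Results will depend on the imaging model, and a rich model may widen intervals. With the 1-year grade alone, the mean 95% CI width at 70%/40% narrowed from 17.6 to 15.5 points (ICC 0.2) and from 21.9 to 17.4 (ICC 0.6). That is close to a best case, because no failed graft was allowed to recover.

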6.2.5 Laboratory Indicators

The results of laboratory indicators will be descriptively summarized by the group.

6.2.6 Bleeding Events

Descriptive statistical analysis will be applied to bleeding events including cerebral hemorrhage and massive gastrointestinal hemorrhage associated with antiplatelet therapy.

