### **5.3.2 Secondary Outcome Measures**

Including:

- 1) MACE-5, defined as a composite of all-cause death, myocardial infarction, stroke, coronary revascularization and hospitalization for unstable angina. The outcome measure is the time to the first occurrence of MACE-5 event from randomization to the last visit.
- 2) MACE-3, defined as a composite of cardiovascular death, myocardial infarction and stroke. The outcome measure is the time to the first occurrence of MACE-3 event from randomization to the last visit.
- 3) All-cause death. The outcome measure is the time to the first occurrence of all-cause death from randomization to the last visit.
- 4) Cardiovascular death. All “undetermined death” will be assumed as “cardiovascular death”. The outcome measure is the time to the first occurrence of cardiovascular death from randomization to the last visit.
- 5) Myocardial infarction, including STEMI, NSTEMI, or silent/unrecognized MI (eg. new pathological Q waves detected by ECG, or new reduced ventricular wall motion detected by UCG during follow-up). The outcome measure is the time to the first myocardial infarction from randomization to the last visit.
- 6) Stroke, including ischemic, hemorrhagic, or unknown type. The outcome measure is the time to the first stroke from randomization to the last visit.
- 7) Coronary revascularization, any repeated PCI or CABG, no matter ischemic driven or not. The outcome measure is the time to the first coronary revascularization from randomization to the last visit.
- 8) Hospitalization for unstable angina. The outcome measure is the time to the first hospitalization for unstable angina from randomization to the last visit.
- 9) Graft failure/vein graft failure at the last visit (Fitzgibbon Grade B/O assessed by CCTA or CAG). The outcome measure is the incidence of graft failure/vein graft failure.

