## **5.4 Safety**

The primary and secondary efficacy outcomes and measures serve as the primary and secondary safety outcomes and measures. Other safety outcome measures include other serious adverse events resulting in hospitalization or emergency visits.

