### **5.4.2 Severe Adverse Events Collection Reports**

In addition to the primary and secondary outcome events, the present study also collect other severe adverse events resulting in hospitalization or emergency visits, which includes cardiac insufficiency, heart failure; arrhythmias, such as atrial fibrillation, atrial flutter, and supraventricular tachycardia; other thrombotic events, such as pulmonary embolism, deep venous thrombosis; neurological diseases, such as Alzheimer's disease, dizziness and vertigo (excluding stroke), tumors; respiratory system diseases, such as pulmonary infection, acute onset of COPD; digestive system diseases, such as gastrointestinal bleeding, tumors; urinary system diseases, such as renal insufficiency, hemodialysis, urinary tract infections, tumors; endocrine system diseases, such as diabetes, tumors; hematological system diseases, such as anemia, tumors; musculoskeletal system diseases, such as fractures, cervical and lumbar diseases, tumors; other unclassified reasons, such as social factors. Physical examination needs do not fall into this category.

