7.1.5 Concomitant medications and bleeding events

Table 15 Concomitant medications during follow-up

Indicator	A	T+A	T	P
Drug1				0.***
N(missing)	*** (***)	*** (***)	*** (***)	
Use	*** (***)	*** (***)	*** (***)	
Not use	*** (***)	*** (***)	*** (***)	
Drug2				0.***
N(missing)	*** (***)	*** (***)	*** (***)	
Use	*** (***)	*** (***)	*** (***)	
Not use	*** (***)	*** (***)	*** (***)	
Ditto for other drugs				

Table 16 Bleeding events during follow-up

Indicator	A	T+A	T	P
Cerebral hemorrhage				0.***
N(missing)	*** (***)	*** (***)	*** (***)	
Occur	*** (***)	*** (***)	*** (***)	
Not occur	*** (***)	*** (***)	*** (***)	
Massive gastrointestinal hemorrhage				0.***
N(missing)	*** (***)	*** (***)	*** (***)	
Occur	*** (***)	*** (***)	*** (***)	
Not occur	*** (***)	*** (***)	*** (***)	

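### The only by-arm bleeding table (SAP Table 16) is narrower than the protocol's safety outcome, so a hospitalized gastrointestinal bleed not called massive is listed but never counted by arm

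*SAP*

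**What the plan says.** **Protocol, what is collected.** Section 5.4 first sets the safety outcomes equal to the efficacy outcomes: "The primary and secondary efficacy outcomes and measures serve as the primary and secondary safety outcomes and measures". It then adds other serious adverse events that lead to hospitalization or an emergency visit as further safety measures. Section 5.4.2 gives the criterion, "the present study also collect other severe adverse events resulting in hospitalization or emergency visits", and its examples include "digestive system diseases, such as gastrointestinal bleeding, tumors". It sets no severity threshold and asks for no link to treatment. Section 5.3.2 defines the stroke outcome as "Stroke, including ischemic, hemorrhagic, or unknown type".

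**SAP, what is compared.** Section 6.2.6 plans descriptive statistics for bleeding events and, after the word *including*, names "cerebral hemorrhage and massive gastrointestinal hemorrhage associated with antiplatelet therapy". The matching shell in section 7.1.5, "Table 16 Bleeding events during follow-up", has columns for the three arms and a P value. Its only rows are cerebral hemorrhage and "Massive gastrointestinal hemorrhage". Section 6.2.7 sends safety events in general to a listing (Table 33).

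**Who judges.** Protocol 7.3 names deaths, myocardial infarction, stroke and revascularization for the independent endpoint committee. Bleeding is not named. Neither document defines massive or associated, gives a bleeding scale, or says who applies these labels.

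**The concern.** Bleeding is the main harm to set against any five-year benefit of the two ticagrelor regimens. The protocol's leading safety outcomes are its efficacy outcomes, so Table 16 carries most of the harm side of the randomized comparison. If its scope is narrower than what the protocol collects, part of the serious bleeding is recorded but not compared.

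Two undefined labels decide what enters the table. A severity label lowers the count and so the precision. An attribution label can also move the ratio in either direction if it is applied unequally across arms. It does not isolate the randomized regimen either: Protocol 3.1 says that after month 12 most subjects would take aspirin and others whatever their physician chose, so a bleed linked to antiplatelet therapy need not be linked to the assigned arm.

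**Working it through.** The documents give no bleeding rate, effect size or power, so there is no stated figure to reproduce. The scope question is settled by comparing the texts. The arithmetic only illustrates possible size.

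**1. Where each kind of serious bleed is reported**

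| Bleed leading to hospitalization or emergency visit | Collected | Counted by arm |
|---|---|---|
| Gastrointestinal, called massive and associated | Protocol 5.4.2 | Table 16 |
| Gastrointestinal, called massive, not associated | Protocol 5.4.2 | Depends on the reading of SAP 6.2.6 |
| Gastrointestinal, not called massive | Protocol 5.4.2 | No; Table 33 listing only |
| Hemorrhagic stroke | Protocol 5.3.2 | Stroke rows of Tables 9 and 10, not split by type; also Table 16, unless the attribution phrase excludes it |
| Other site | Only under a general or unclassified heading of 5.4.2 | No; listing only |

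The third row holds on every reading of SAP 6.2.6. Table 16 has no line extending it to further bleed types, whereas Tables 14, 15 and 17 each say that other indicators, drugs or subgroups follow in the same way.

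**2. Illustration: unequal attribution**

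Inputs: arm sizes 168 (T+A) and 166 (A), from Protocol 9.3. Serious-bleed rates of 6% and 4% and the attributed shares are assumptions.

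- Expected counts: 168 × 0.06 = 10.08 and 166 × 0.04 = 6.64.
- Risk ratio: 0.06 / 0.04 = 1.50. This uses the unrounded counts; whole counts of 10 and 7 give (10/168) / (7/166) = 1.41.
- SE of log RR = √(1/10.08 − 1/168 + 1/6.64 − 1/166) = 0.488. The 95% CI is 1.50 ÷ and × exp(1.96 × 0.488), or 0.58 to 3.9.
- Observed RR = true RR × (share attributed in T+A ÷ share attributed in A):
  - 90% and 60%: 1.50 × 0.9/0.6 = 2.25
  - 60% and 90%: 1.50 × 0.6/0.9 = 1.0
  - 60% in both: 1.50. Counts fall to 6.05 and 3.98, the SE rises to 0.636, and the CI widens to 0.43 to 5.2.
- With a true RR of 1.0, shares of 90% and 50% give 1.80, and 70% and 90% give 0.78.

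**3. Illustration: lost events**

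Assume a true risk ratio of 2 and a two-sided 5% level, with the same arm sizes. Half of all bleeds are lost, equally in both arms.

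| Rate in A (assumed) | Events, all counted | Power | Events, half counted | Power |
|---|---|---|---|---|
| 2% | 10 | 0.19 | 5 | 0.11 |
| 4% | 20 | 0.34 | 10 | 0.19 |
| 6% | 30 | 0.48 | 15 | 0.26 |

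**The case against.** **Wording.** In SAP 6.2.6 the two bleed types follow the word *including*, which need not be exhaustive. The attribution phrase may qualify the gastrointestinal bleeds alone, and the rows of Table 16 do not repeat it. This stands: the limit to two types comes from the table shell, and an attribution filter on all bleeds is only one reading.

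**Blinding.** A reader might infer that bleeds are attributed by people who know the arm, because the parent trial was open label. The documents do not support that. They name no assessor, and SAP section 3 describes the parent trial as evaluator blind. What can be said is that the assessor and the blinding are not stated.

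**Coverage elsewhere.** A reader might also infer that the other serious bleeds vanish. They do not. Hemorrhagic stroke is counted by arm within stroke whatever its cause, and non-fatal stroke goes to the committee. Fatal bleeds count in all-cause death, and safety events are listed. This stands and narrows the gap to the by-arm count, mainly of gastrointestinal bleeds.

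**Size.** All three regimens were antiplatelet therapy, so strongly unequal attribution is not an obvious default. The unfiltered interval of 0.58 to 3.9 already contains 1.0, 1.5 and 2.25, and power is below one half even with every bleed counted. This stands: the fix would improve description and would seldom change a formal conclusion. Bleeding is also not a stated objective, and its analysis is labelled descriptive.

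**Feasibility.** Section 5.4.2 describes collection in the present study. It does not show that year-1 bleeds are held in the same form, and it names no bleeding site except gastrointestinal. This stands and limits what the fix can ask for.

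None of these points gives a by-arm count to a hospitalized gastrointestinal bleed that is not called massive.

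**Conclusion.** The point holds as a mismatch of scope. SAP 6.2.6 and Table 16 are narrower than the safety outcome in Protocol 5.4 and 5.4.2, and they rest on two undefined labels with no stated assessor. The gap certain on any reading is serious gastrointestinal bleeds not called massive. On one reading it extends to bleeds not called associated. A cerebral bleed could then count as a stroke and be missing from Table 16.

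The documents do not show that a causality filter applies to every bleed, that it is applied unblinded, or that the comparison is biased in a given direction. The figures above rest wholly on assumed rates and shares; they show that the restriction can matter, not that it will. The primary MACE-4 analysis is unaffected. The change is worth making because it completes the harm side of the randomized comparison at little cost.

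**What to change.** In SAP 6.2.6 and Table 16:

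- Tabulate by randomized arm every bleed leading to hospitalization or an emergency visit that was collected under Protocol 5.4.2 or recorded as hemorrhagic stroke, whatever its attribution or severity label.
- Give rows for any serious bleed, cerebral, gastrointestinal, and other (if any are recorded). Show n (%), the risk difference and its 95% CI for each.
- Keep massive bleeds and attributed bleeds as sub-rows. Define both terms, and state who assigns them and whether that person is blind to arm.
- Count from randomization where year-1 bleeds are available from the parent trial's database. Otherwise state the period covered.
- Reconcile the descriptive label in 6.2.6 with the P column of Table 16.

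The cost is SAP wording and one larger table, built on data the protocol already collects, plus a check of what the parent trial holds for year 1. Bleeding counts may look less favourable. With few events the intervals will be wide: at the assumed 6% and 4%, the risk difference is 2.0 percentage points with SE √(0.06 × 0.94/168 + 0.04 × 0.96/166) = 2.4 points, so a 95% CI of about −2.7 to 6.7.
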